11.6 Population analysis of pharmacokinetic/pharmacodynamic variables

AZD6140 and its active metabolite AR-C124910XX concentrations in plasma, which will be measured for the studied population in this study, will be served for population PK analysis.

The result of population analysis of PK/PD will be reported separately from CSR.

11.7 Calculation or derivation of pharmacogenetic variables – Not applicable

11.8 Calculation or derivation of health economic variables – Not applicable

12. STATISTICAL METHODS AND SAMPLE SIZE DETERMINATION BY ASTRAZENECA

Statistical analyses will be performed by Statistics & Programming Department, AstraZeneca KK using SAS. The SAP will provide further details of the analyses and presentation of the data. The SAP will be finalised before the database lock.

12.1 Description of analysis sets

Patient inclusion in each of the analysis sets will be determined before database lock. Throughout the analyses, erroneously treated subjects (eg, those randomised to treatment A but actually given treatment B) will be accounted for in the actual treatment group.

12.1.1 Pharmacodynamic analysis set

All randomised patients who received at least one dose of investigational product with post-dose PD measurements available and no protocol deviation/violation considered to significantly affect PD of AZD6140 will be included in PD analysis set

12.1.2 Pharmacokinetic analysis set

All randomised patients who received at least one dose of investigational product with post-dose PK measurements available and no protocol deviation/violation considered to significantly affect PK of AZD6140 and its metabolite, AR-C124910XX, will be included in PK analysis set.

12.1.3 Safety analysis set

All subjects who received at least one dose of randomised investigational product will be included in the safety analysis set.

12.2 Methods of statistical analyses

12.2.1 Pharmacodynamic data

All PD data will be listed by patient and summarised by region (Japan, non-Japan) and treatment group.

At each time point, all PD variables will be summarised using the following descriptive statistics.

- N
- Arithmetic mean
- SD
- Median
- Minimum
- Maximum

The mean and individual plots of PD variables over time by day will be presented.

IPA (final extent) at 2, 4, 8, 12 and 24 hours post-dose on Day 28 will be analysed separately based on ANOVA model including treatment group (AZD6140 45mg, 90mg and clopidogrel) and the difference between AZD6140 dose groups and its 2-sided 95% confidence interval will be estimated. In addition, the difference between each AZD6140 dose group and clopidogrel group and its 2-sided 95% confidence interval will be estimated.

The plots of IPA against plasma concentration of AZD6140 and AR-C124910XX will be made. Exploratory analyses based on non-linear models such as sigmoid E-max model will be made to investigate the relationship between PK and PD.

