1.4 Benefit/risk and ethical assessment

The Investigator's Brochure (IB) for AZD6140 contains the information supporting the overall risk/benefit assessment of the investigational agent and is available as a reference for investigators. It contains a summary of all the relevant pharmaceutical, nonclinical and clinical findings with AZD6140.

AZD6140 is intended for use to prevent the thrombotic complications (cardiovascular death, MI, and stroke) associated with ACS and its sequelae. Aspirin, and clopidogrel in combination with aspirin, have been shown to reduce the risk of these complications with acceptable benefit/risk profiles. Despite the established incremental efficacy of clopidogrel over aspirin alone, its requirement for metabolic activation (slow onset of action), irreversibility (slow offset of action with prolonged period of partial blockade) and high degree on inter-patient variability in the IPA (with an inadequate IPA response in up to 31% of patients undergoing PCI) ([Gurbel PA et al 2003](#)) underscore the need for a better agent. The more modest effects

on platelet aggregation, and the larger inter-patient variability of effect, of clopidogrel compared to newer agents like AZD6140 suggests that the risk for such events can be further substantially reduced.

Previous studies show that administration of AZD6140 results in substantially higher levels (more than 20% mean absolute increase) of *ex vivo* IPA with less variability compared to clopidogrel (with or without ASA background therapy).

The result from the PLATO showed that AZD6140 statistically significantly decreased the incidence of thromboembolic events (death from vascular causes, non-fatal myocardial infarction and non-fatal stroke) in ACS patients, compared to clopidogrel, demonstrating the greater preventive effect of AZD6140 on thromboembolic events without increased Major bleeding risk.

Ideally, it is preferable to recruit patients in a Phase II Asian collaboration study who are as closer to the target population for which AZD6140 will be ultimately indicated as possible. However, 90 mg bid is to be the therapeutic dose and 45 mg bid may not be clinically effective enough, it is considered inappropriate to enrol patients to whom dual antiplatelet therapy with ASA is essential.

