11.5 Calculation or derivation of pharmacodynamic variable(s)

Maximum and final extent IPA from pre-dose baseline at Visit 2 will be calculated at all subsequent timepoints using the following formula for ADP-induced platelet aggregation:

$$\text{Percentage Inhibition} = 100\% \times (PAs - PA) / (PAs)$$

PA is the mean response at the given post dose time point and PAs is the mean response at pre dose baseline. Percentage inhibition will be restricted to the closed interval [0,100]; any data falling outside this range will be truncated to the appropriate limit.

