12.3 Determination of sample size

The sample size is not based on formal statistical tests. As a measure of study precision, with 34 Japanese patients per group, the expected width of the 2-sided 95% confidence interval of the difference between 90mg and 45mg dose groups in IPA is approximately $\pm 12\%$, assuming the SD for the final IPA of 25% based on DISPERSE.

In order to obtain PK and PD data in non-Japanese Asian patients and to make exploratory comparison between Japanese and non-Japanese Asian, 7 non-Japanese Asian patients per group will be included. Based on DISPERSE, the difference between the higher dose (90mg) and lower dose (45mg) in final IPA at 12 hours post-dose at Week 4 was predicted to be at least 12%. With 7 non-Japanese Asian patients per group, $P(D_{NJP} > 0)$, where D_{NJP} is estimate of difference between 90mg and 45mg dose groups in IPA for non-Japanese Asian is more than 0.8. Therefore, 7 non-Japanese Asian patients per group is considered sufficient to obtain consistent result in terms of point estimates.

Assuming that there are approximately 10% premature discontinuations due to informed consent withdrawal and/or AE, 45 patients per group to be randomized in total.

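### The three-arm Day 28 ANOVA ordinarily pools one variance, although the protocol says IPA is less variable on AZD6140 than on clopidogrel

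*Protocol*

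**What the plan says.** Protocol Section 12.2.1 analyses final-extent IPA separately at 2, 4, 8, 12 and 24 hours on Day 28, "based on ANOVA model including treatment group (AZD6140 45mg, 90mg and clopidogrel) and the difference between AZD6140 dose groups" with its 2-sided 95% confidence interval. From the same model, "the difference between each AZD6140 dose group and clopidogrel group and its 2-sided 95% confidence interval will be estimated". No other model term and no variance structure is named. Section 12 leaves further detail to the SAP.

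Section 1.4 says that AZD6140 gives "IPA with less variability compared to clopidogrel", and in the preceding paragraph attributes a larger inter-patient variability to clopidogrel. Section 1.1 also reports wide variability of IPA among Japanese patients on clopidogrel.

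Section 12.3 sizes the trial by interval width: "with 34 Japanese patients per group, the expected width of the 2-sided 95% confidence interval" for the dose difference is about ±12%, "assuming the SD for the final IPA of 25% based on DISPERSE". This single SD is the only one given.

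Section 11.5 defines IPA relative to the Visit 2 pre-dose value, where "PAs is the mean response at pre dose baseline", and truncates it to 0-100%.

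**The concern.** An ordinary ANOVA over three arms estimates one residual SD and uses it for every pairwise difference. If clopidogrel is the most variable arm, its variance inflates the interval for 90 mg minus 45 mg, a contrast in which clopidogrel takes no part. In the other direction, the smaller AZD6140 variances shrink one or both of the intervals against clopidogrel.

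These intervals are the trial's main inferential output. Section 12.3 justifies the sample size by interval width and not by a test, so whether a 95% interval really covers 95% matters. The dose contrast serves the primary objective (Section 2.1), and the clopidogrel contrasts serve secondary objective 9 (Section 2.2).

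**Working it through.** **Inputs from the protocol.** n = 34 per arm, 2-sided 95% and a common SD of 25 (Sections 12.2.1 and 12.3). **Assumed:** all SDs by arm, because the protocol gives none.

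**1. The plan's own figure.** Half-width = critical value × SD × √(2/n).
- Normal: 1.960 × 25 × √(2/34) = 1.960 × 25 × 0.2425 = 11.88.
- t with 99 df (three-arm ANOVA): 1.984 × 25 × 0.2425 = 12.03.

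Both agree with the stated ±12%.

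**2. Direction of the error.** The pooled variance is (s45² + s90² + sC²)/3. A contrast between two arms needs the mean of those two variances. The pooled interval is therefore too wide when the third arm's variance exceeds that mean, and too narrow when it falls below.
- 90 mg minus 45 mg: too wide if sC² > (s45² + s90²)/2, which always holds when clopidogrel has the largest SD.
- 45 mg versus clopidogrel: too narrow if s90² < (s45² + sC²)/2.
- 90 mg versus clopidogrel: too narrow if s45² < (s90² + sC²)/2.

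If clopidogrel has the largest SD, at least one of the last two conditions must hold. Both need not.

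**3. Size of the error.** Pooled half-width = 1.984 × √[(s45² + s90² + sC²)/3] × √(2/34). Separate-variance half-width = t(ν) × √[(si² + sj²)/34], with ν from Satterthwaite. Coverage of the pooled interval comes from simulation of normal data, at least 40,000 trials per row. Each contrast cell shows the separate-variance half-width, then the coverage of the pooled interval.

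| SDs 45 mg/90 mg/clopidogrel | Pooled half-width | 90 mg − 45 mg | 45 mg − clopidogrel | 90 mg − clopidogrel |
|---|---|---|---|---|
| 25/25/25 | 12.03 | 12.11; 95% | 12.11; 95% | 12.11; 95% |
| 20/20/25 | 10.49 | 9.68; 97% | 10.97; 94% | 10.97; 94% |
| 20/15/25 | 9.82 | 8.57; 98% | 10.97; 92% | 10.02; 95% |
| 20/20/30 | 11.46 | 9.68; 98% | 12.38; 93% | 12.38; 93% |
| 25/15/30 | 11.62 | 10.02; 98% | 13.38; 91% | 11.56; 95% |

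Separate-variance intervals cover 95% in every row. In the unequal rows the pooled dose-contrast interval is 8% (10.49/9.68) to 18% (11.46/9.68) too wide.

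**4. Hand check of the last row.** Pooled SD = √[(625 + 225 + 900)/3] = 24.15, so the half-width is 1.984 × 24.15 × 0.2425 = 11.62. The true standard error for 45 mg versus clopidogrel is √[(625 + 900)/34] = 6.70. Then 11.62/6.70 = 1.735, and 2Φ(1.735) − 1 = 0.917, close to the simulated 91%.

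**5. Baseline covariate.** With correlation ρ between baseline aggregation and Day 28 IPA, and SD 25, half-width = t(98) × 25 × √(1 − ρ²) × √(2/34) × √(1 + 1/98). This gives 12.09 at ρ = 0, 12.03 at 0.1, 11.54 at 0.3 and 10.47 at 0.5, against 12.03 without the covariate. Break-even is near ρ = 0.1. The protocol gives no ρ. An illustrative simulation in which the drug removes a fraction of baseline aggregation (all values assumed) gave ρ from 0.00 to 0.16.

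**The case against.** **The variance structure is not stated.** Pooling is inferred from the word ANOVA, and the SAP could specify otherwise. That is a fair limit on the claim. But the model itself is fixed in the protocol and a single variance is its ordinary meaning. The single SD in Section 12.3 fits that reading. So this is a stated method that conflicts with the protocol's own background, and not merely a missing detail.

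**Section 1.4 is weak evidence about 45 mg.** Its sentence on lower variability concerns regimens with IPA more than 20% above clopidogrel, whereas Section 1.3 reports that 50 mg twice daily, equivalent to 45 mg, gave IPA similar to clopidogrel. This stands. The first two contrasts are still mis-sized if 45 mg is as variable as clopidogrel and only 90 mg is less so. With assumed SDs of 25/10/25, coverage is 97.0% for the dose contrast and 90.4% for 45 mg versus clopidogrel. In that case 90 mg versus clopidogrel is too wide, also at 97.0%.

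**The consequences are limited.** The error on the primary contrast is conservative. Section 3.2 says the study is not confirmatory of DISPERSE, Section 12.3 rests on no formal test, and Section 12.2.1 already reports the SD by arm, so unequal spread will be visible. All of this stands and keeps the point modest.

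**Stronger readings that the documents do not support.** A reader might infer that the ±12% or the sample size is wrong. It is right under its own common SD. A reader might infer that every clopidogrel interval under-covers. The one for 90 mg can be about correct. A reader might also infer that omitting baseline wastes precision. Baseline is already the denominator of IPA, its remaining correlation with IPA is not given, and the gain may be close to nil.

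**Conclusion.** The point holds, conditionally. If IPA is more variable on clopidogrel than on AZD6140, as Section 1.4 says, an ordinary pooled ANOVA makes the 90 mg minus 45 mg interval too wide and at least one clopidogrel interval too narrow. Over the assumed SDs from 20/20/25 to 25/15/30 at 34 per arm, coverage is about 97-98% for the dose contrast, 91-94% for 45 mg versus clopidogrel and 93-95% for 90 mg versus clopidogrel. With equal SDs there is no error.

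This rests on the usual pooled reading of ANOVA, on assumed arm SDs and on normal data, whereas IPA is truncated at 0 and 100%. With arms of equal size, the relative widths depend on n only slightly, through the t multiplier. The matter is one of interval calibration in an estimation study. No stated figure, power or decision rule is wrong.

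**What to change.** In Section 12.2.1, state that each Day 28 contrast is estimated from a model with treatment group as a fixed effect, a separate residual variance for each treatment group and Satterthwaite degrees of freedom. Keep the plain ANOVA as a sensitivity analysis.

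The change is one sentence and one model option in SAS. If SDs are equal, the interval widens from 12.03 to 12.11, under 1%. If they are unequal, the 45 mg versus clopidogrel interval widens by up to about 15% (13.38/11.62 = 1.15), which is its honest width, and the dose-contrast interval becomes narrower.

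Visit 2 pre-dose aggregation is already collected and may be added as a pre-specified covariate. It costs one degree of freedom, about 0.5% in width if it is uncorrelated with Day 28 IPA (12.09 against 12.03). The text should not promise a precision gain.

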12.2.2 Plasma concentration of AZD6140 and AR-C124910XX

All plasma concentration data will be listed by patient and summarised by region and treatment group.

At each time point, all plasma concentrations will be summarised using the following descriptive statistics.

- N
- Number of samples \geq Lower limit of quantification (LOQ)
- Geometric mean
- CV (calculated as $100 \times \sqrt{(\exp(s^2)-1)}$, where s is the standard deviation of log transformed sample values)
- Arithmetic mean
- SD
- Median
- Minimum
- Maximum

The handling of plasma concentrations below LOQ will be specified in the SAP.

The mean and individual plots of plasma concentration of AZD6140 and AR-C124910XX over time by day will be presented.

12.2.3 PK parameters

All PK parameters will be listed by patient and summarised by region and treatment group.

All PK parameters except for t_{\max} will be summarised by day using the following descriptive statistics.

- N
- Geometric mean
- CV (calculated as $100 \times \sqrt{(\exp(s^2)-1)}$, where s is the standard deviation of log transformed sample values)
- Arithmetic mean

- SD
- Median
- Minimum
- Maximum

For t_{\max} , the following descriptive statistics will be presented.

- N
- Median
- Minimum
- Maximum

12.2.4 Safety data

All safety variables will be listed by patient and summarised descriptively by treatment group.

All AEs will be listed and summarised by the System Organ Class and Preferred Terms assigned to the events using MedDRA vocabulary. Furthermore, listings of SAEs and AEs that led to withdrawal will be made and the number of patients who had any AEs, SAEs, AEs that led to withdrawal, and AEs with severe intensity will be summarised. If appropriate, adverse drug reactions will be summarised by the System Organ Class and Preferred Term assigned to the event using the MedDRA.

For the bleeding events adjudicated by CEC, the number of patients with bleeding event along with percentage will be presented.

For the quantitative safety variables, the observed value and the changes from baseline at each time point will be summarised using the following descriptive statistics.

- N
- Arithmetic mean
- SD
- Minimum
- Median
- Maximum

For all quantitative safety variables, the baseline will be the pre-dose value at Day 1. If a patient has more than 1 observation on the same measurement occasion, the results from the earliest draw should be used in all summaries.

For qualitative safety variables, shift tables at each time point will be presented.

Laboratories values outside the reference range will be listed.

12.3 Determination of sample size

The sample size is not based on formal statistical tests. As a measure of study precision, with 34 Japanese patients per group, the expected width of the 2-sided 95% confidence interval of the difference between 90mg and 45mg dose groups in IPA is approximately $\pm 12\%$, assuming the SD for the final IPA of 25% based on DISPERSE.

In order to obtain PK and PD data in non-Japanese Asian patients and to make exploratory comparison between Japanese and non-Japanese Asian, 7 non-Japanese Asian patients per group will be included. Based on DISPERSE, the difference between the higher dose (90mg) and lower dose (45mg) in final IPA at 12 hours post-dose at Week 4 was predicted to be at least 12%. With 7 non-Japanese Asian patients per group, $P(D_{NJP} > 0)$, where D_{NJP} is estimate of difference between 90mg and 45mg dose groups in IPA for non-Japanese Asian is more than 0.8. Therefore, 7 non-Japanese Asian patients per group is considered sufficient to obtain consistent result in terms of point estimates.

Assuming that there are approximately 10% premature discontinuations due to informed consent withdrawal and/or AE, 45 patients per group to be randomized in total.

12.4 Data safety monitoring board

In this study, a single joint DSMB will be established for this study and the clinical Phase III study (D5130C00027), which are conducted separately.

The DSMB is independent of AstraZeneca and study sites, and will monitor the progress of all aspects of the study (eg, efficacy and safety) and will ensure that the study meets the highest standards of ethics and patient safety.

The DSMB will bear the primary responsibility for monitoring of study data for adverse trends in mortality, morbidity, and drug safety in these two studies.

In this study, the DSMB will review all cardiac ischaemic events and all AEs/SAEs (including stroke) under an unblind fashion at least every 3 months to determine the appropriateness of continuing the study.

In addition to the periodical review during this study, the DSMB will discuss whether a Phase III study can be initiated, based on the data from this study. Also, after the Phase III study is initiated, the DSMB will review the data from the Phase III study together with the data from this study, and perform a comprehensive safety assessment similar to the periodical review in

accordance with the time point defined for the Phase III study to determine the appropriateness of continuing these two studies.

To accurately facilitate this review, clinical events of special interest will be reported by the investigator as soon as possible via the eCRF, and clinical laboratory data and the 24-hour holter ECG data will be supplied by the central vendors to the investigator and AstraZeneca Data Management. These events include suspected cardiac ischaemic events, symptomatic possible bradycardia events, pacemaker use and major bleeding events.

A recommendation by the DSMB to stop the study for adverse effects observed in the AZD6140 treatment arm may be at any time. Criteria for determination of the appropriateness of continuing studies will be separately detailed in the DSMB Charter.

12.5 Clinical Endpoint Committee

In this study, a single joint CEC will be established for this study and the clinical Phase III study (D5130C00027), which are conducted separately.

The CEC is independent of AstraZeneca, study sites and DSMB, and the CEC is to independently review and interpret the bleeding events that are reported by the investigator as defined in Section 6.4.9.1. This will provide a consistency of interpretation of the events across sites and countries participating in the study. The CEC will implement streamlined, efficient processes of blinded adjudication of reported events.

If the results centrally adjudicated by the CEC are different from those by the investigator, the CEC-adjudicated results will be used for analyses.

Responsibility of the CEC and procedure of central adjudication will be separately detailed in the CEC Charter.

13. IMPORTANT MEDICAL PROCEDURES TO BE FOLLOWED BY THE INVESTIGATOR

13.1 Medical emergencies and AstraZeneca contacts

The principal investigator(s) is responsible for ensuring that procedures and expertise are available to handle medical emergencies during the study. **A medical emergency usually constitutes an SAE and should be reported as such, see Section 6.4.4.**

In the case of a medical emergency the investigator may contact the Study Delivery Team Leader. If the Study Delivery Team Leader is not available, contact the Study Delivery Team Physician/other physician at the AstraZeneca Research and Development.

Name	Role in the study	Address & telephone number
	Study Delivery Team Leader responsible for the protocol at central R&D site	Tel: Fax: Mobile:
	SDT Physician responsible for the protocol at central R&D site	Tel: Fax: Mobile:
(For Japan) Monitor	Study Delivery Team monitor	See Supplement A, “Investigations and Study Administrative Structure”

The treatment code may not be broken unless in an emergency situation where appropriate management of the patient necessitates knowledge of the treatment allocation. If possible, investigators should contact AstraZeneca or designee before breaking the treatment code.

There is no known antidote to reverse the effects of AZD6140. The average half-life of AZD6140 is approximately 12 hours, so blood levels of AZD6140 should be low by 48 to 72 hours (ie, 4 to 6 half-lives) after discontinuation. Platelet transfusions may be given, but new platelets may be inhibited by AZD6140 as long as it is circulating in blood.

13.1.1 Major bleeding events

Major bleeding events should be managed according to need with general support and blood products.

If platelet transfusion is considered, the treatment code should be broken only if deemed necessary by the investigator (see Section 5.4.2 for unblinding procedures) since this approach will likely not reverse the effects of AZD6140. It is understood that new platelets are likely to be inhibited by AZD6140 as long as it is circulating in the blood.

If treatment with DDAVP, aprotinin, recombinant activated Factor VII or other haemostatic agents is to be used, it should not be necessary to break the treatment code.

If a patient experiences a major bleed as defined in Section 6.4.9.1, study medication should be discontinued.

